- Catheter ablation for right-sided typical atrial flutter during the time period. This will be determined by the presence of an endocardial catheter ablation recorded on the Rhythm Disturbance Evaluation eCRF where the date performed falls within the time period of interest. Catheter ablation location (left, right, or other/indeterminate) will be determined as described in Section 7.4.6. Catheter ablation for right-sided typical atrial flutter will be categorized as those marked as being performed for "Other SVT" where the location is categorized as right side, or performed for "Typical AFL (Right Atrial)".

7.4.6 Catheter Ablation

Catheter ablation date and location(s) (as a free text field) are collected on the Rhythm Disturbance Evaluation eCRF page. Prior to database lock and subsequent unblinding of study sponsor, a list of ablation locations will be tabulated and provided to the Medical Monitor or designee for categorization of ablation location. Possible categorizations will include: Left, Right, Other, or Indeterminate. This list will not include subject identifiers or treatment arm. This information will be finalized prior to database lock, and incorporated into analysis datasets in order to determine if subjects meet criteria for treatment failure based on left or right side cardiac ablations as specified in Section 9.1.

8 STUDY POPULATION

Unless otherwise noted, the Safety Population will be used for summaries of the study population.

8.1 Subject Disposition

Subject disposition will be presented for all subjects. The subject disposition listing will include the date of study completion (at approximately 12 months post treatment) or withdrawal, whether the study was completed per protocol (for both main study period and long-term follow-up), reason for withdrawal, date of last contact, and documentation of attempts to contact the subject. The listing of analysis populations will include whether the subject was included in each analysis population and the reason for exclusion. The number of subjects in each population, number of subjects who completed the study, number of subjects who discontinued from the study, number of intra-op exclusion failures, and reasons for study discontinuation will be summarized.

8.2 Informed Consent and Inclusion/Exclusion Criteria

The informed consent listing will include whether the informed consent was completed appropriately, date of informed consent, and protocol version date. The inclusion/exclusion criteria listing will include whether or not the subject was eligible to participate, inclusion/exclusion criteria failed, whether or not the subject qualified for randomization, and randomized treatment arm.

8.3 Protocol Violations

Protocol violations/deviations will be recorded on the eCRF, and categorized as inclusion/exclusion criteria, informed consent issue, out of window visit, protocol-required evaluation not completed, or other (with additional information specified). The date of the violation, description, and corrective action (if applicable) will also be recorded.

Prior to database lock and subsequent unblinding of study sponsor, a list of violations will be provided to the Medical Monitor or sponsor designee for determination of major protocol violations. The designations of major or minor violation will be finalized prior to database lock and subsequent unblinding of study sponsor, and incorporated into analysis datasets. Major protocol violations will be identified in data listings.

Protocol violations (both major and minor) and major protocol violations will be summarized by category and treatment arm.

8.4 Demographic and Other Baseline Characteristics

The demographics and baseline characteristics listing will include date of birth, age, gender, race, ethnicity, height, weight, body mass index (BMI), presence of persistent AF vs long-standing persistent AF, and smoking history (never smoked, past smoker, current smoker, unknown).

Gender, ethnicity, race, BMI, and smoking history will be summarized descriptively by treatment arm and overall. Age, weight, and height will each be summarized continuously by treatment arm and overall.

Demographics and baseline characteristics of subjects with missing data will be compared between the two treatment arms, as well as to those subjects without missing data, to explore whether there are any factors associated with having missing data. Gender, ethnicity, race, age, persistent vs. long-standing persistent AF, and BMI will be compared between the treatment arms, separately for subjects whose AT/AF/AFL freedom needs to be imputed as per Section 7.2 (i.e. those with missing information for the primary efficacy endpoint) and those whose information is not missing. Fisher's exact test will be used to compare gender, ethnicity, and persistent AF. Race will also be compared using the Fisher's Exact test, with subjects grouped into White or Non-white categories. Age and BMI will be compared using a Student's t-test or the Wilcoxon rank sum test. Smoking history (treating unknown values as missing) will be compared using the chi-square test.

Demographic and baseline characteristics will similarly be compared between those with missing information for the primary endpoint (those having an indeterminate result for AF/AFL/AT status, as described in Section 7.4.5; imputation as described in Section 7.2 will not be applied for this comparison) and those without, after pooling treatment arms within each of the two groups.

8.5 Medical History

Medical history will be listed by subject and body system. The number of subjects with any medical history will be summarized for overall medical history and by body system, by treatment arm and overall.

Cardiac history will be listed by subject, date, and aneurysm location (if applicable). The number of subjects with cardiac history will be summarized by cardiac history type, by treatment arm and overall.

Cardiac interventions will be listed by subject, procedure, and date.

Cardioversion history over the previous 12 months will be listed by subject, date, and cardioversion type. The number of cardioversions during that period will be summarized by cardioversion type, by treatment arm and overall.

Documentation of persistent AF and other AF history will be listed by subject. The number of years in AF, and AF associated symptoms over the last 12 months will be summarized by treatment arm and overall.

8.6 Non-Study Medications

All class I, II, III, and IV AADs, as well as other cardiac and anti-coagulants taken by the subject prior to and during study enrollment, will be recorded on the eCRF. All recorded non-study medications that are halted prior to the study procedure date will be classified as prior medications. Medications taken on or after the date of study procedure, including those taken both before and after the procedure, will be categorized concomitant. If insufficient information is available to definitively categorize a medication, it will be considered concomitant. No standardized classification of medications (such as using a drug dictionary) is currently planned.

All medications will be listed by subject. Prior medications will be indicated in the listing. Class I/III AADs will also be flagged in data listings, as well as presented in a separate listing. No summaries of medications will be presented.

8.7 Pre-Procedure and Procedure Data

Different pre-procedure and procedure data are collected for subjects in each treatment arm. Therefore, these listings will be presented separately for subjects in each treatment arm. Subjects undergoing pre-procedure assessments, who discontinue prior to study procedure, will be included in study listings, and flagged as not having undergone study procedure. Similar, summaries of pre-procedure and procedure data will be presented separately by treatment arm, where applicable.

9 EFFICACY ANALYSES

The ITT population will be used as the primary analysis population for efficacy analyses. The mITT and PP populations will be used for sensitivity analyses as described. Efficacy summaries and analyses will be presented by treatment arm.

In case of sparsity of cells (when the table consists of a cell where the expected number of frequencies is fewer than 5), Fisher's Exact test will be utilized instead the chi-square test for a 2x2 table for the primary and secondary efficacy endpoints.

9.1 Primary Efficacy Analysis

The binary primary endpoint of success or failure to achieve freedom from AF/AT/AFL absent class I and III AADs except for a previously failed or intolerant class I or III AAD with no increase in dosage following the 3 month blanking period through the 12 months post procedure follow-up visit will be compared between the two treatment groups using a chi-square test using a two-sided alpha of 0.05 to determine if superiority of the treatment arm is attained. This is detailed in Sections 2.3.1 and 7.4.5 of the SAP.

The analysis will be performed on the ITT population. If necessary, imputation will be performed as specified in Section 7.2.

Define P as the true percentage of subjects failing to achieve AF/AFL/AT freedom, where P_T is the true failure rate for the treatment arm and P_C for the control arm. The hypothesis to test is:

$$H_0: P_T = P_C \quad \text{vs} \quad H_a: P_T \neq P_C$$

The formula for the chi-square test is:

$$\chi^2 = \sum_{i=1}^n \frac{(O_i - E_i)^2}{E_i}$$

where O_i represents the number of observed events in the i^{th} cell and E_i represents the expected number of events in the i^{th} cell. H_0 is rejected in favor of H_a if the resulting p-value < 0.05 and the estimated P_T exceeds P_C . If $E_i < 5$ for any cell (that is, if the [number of subjects in a treatment arm * total number of successes / total number of subjects] is < 5 , or similarly for the number of failures), then the Fisher's Exact test will be used in lieu of the chi-square test.

If the $p \leq 0.05$, we will conclude that the percentages differ significantly between treatment arms.

The number and percent of subjects achieving AF/AFL/AT freedom will be summarized by treatment arm, and individual results listed by subject.

The primary efficacy analysis will be repeated on the specific subgroups as described in Section 6.3.

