## 9.4 Primary Efficacy Endpoint Analysis

The binary primary endpoint of success or failure to achieve freedom from AF/AT/AFL absent class I and III AADs except for a previously failed or intolerant class I or III AAD with no increase in dosage following the 3 month blanking period through the 12 months post procedure follow-up visit will be compared between the two treatment groups using a chi-square test using a two-sided alpha of 0.05 to determine if superiority of the treatment arm is attained.

Define  $P$  as the true percentage of subjects failing to achieve freedom. The hypothesis to test is:

$$H_0: P_T = P_C \quad \text{vs} \quad H_a: P_T \neq P_C$$

where  $P_T$  is the true failure rate for the Treatment arm and  $P_C$  for the Control arm. The formula for the chi-square test is:

$$\chi^2 = \sum_{i=1}^m \frac{(O_i - E_i)^2}{E_i}$$

where  $O_i$  represents the number of observed events in the  $i$ th cell and  $E_i$  represents the expected number of events in the  $i$ th cell.  $H_0$  is rejected in favor of  $H_a$  if the resulting p-value  $<0.05$  and the estimated  $P_T$  exceeds  $P_C$ .

---

Subjects who were randomized but have no post-treatment assessments will be conservatively imputed as therapeutic failures at six months.

A tipping point analysisx will be conducted to explore the sensitivity of the results to the effect of missing data. Baseline demographics of subjects with missing data will be compared between the two treatment arms, as well as to those subjects without missing data, to explore whether there are any factors associated with having missing data.

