2.1.1 Primary Efficacy Objective

The primary objective is to demonstrate superiority of the experimental convergent procedure (EPi-Sense-AF) compared to the stand-alone endocardial catheter ablation (control) on overall success, defined as freedom from AF/AFL/AT (atrial fibrillation/atrial flutter/atrial tachycardia) absent Class I or III anti-arrhythmic drugs (AADs), except for previously failed Class I or III AADs with no increase in dosage, following the 3 month blanking period through the 12 months post-procedure follow-up visit.

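### The primary superiority rule has its inequality reversed: P is the failure rate, yet rejection requires the treatment failure rate to exceed control

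*SAP*

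**What the plan says.** SAP 9.1 sets up the primary comparison in four steps.

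- **Purpose.** The two arms are compared "using a chi-square test using a two-sided alpha of 0.05 to determine if superiority of the treatment arm is attained".
- **Parameter.** "Define P as the true percentage of subjects failing to achieve AF/AFL/AT freedom". The subscripts mark the arms, so P_T and P_C are the failure rates on the convergent procedure and on catheter ablation.
- **Hypotheses.** H0: P_T = P_C against Ha: P_T ≠ P_C.
- **Rejection rule.** H0 is rejected in favour of Ha "if the resulting p-value < 0.05 and the estimated P_T exceeds P_C".

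A later sentence in the same section adds that, at p ≤ 0.05, "we will conclude that the percentages differ significantly between treatment arms". It names no direction.

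Protocol 9.4 has the same structure. P is defined "as the true percentage of subjects failing to achieve freedom", again with one such rate per arm. The rejection sentence again requires p < 0.05 together with an estimated P_T that exceeds P_C.

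The objective in SAP 2.1.1 is framed on success, not failure: "The primary objective is to demonstrate superiority of the experimental convergent procedure (EPi-Sense-AF) compared to the stand-alone endocardial catheter ablation (control) on overall success". Protocol 1.4.1 says the same. The sample size sections (Protocol 9.2, SAP 4) assume success of 65% on the convergent procedure and 40% on control. SAP 13, which lists departures from the protocol analyses, does not mention the rule.

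**The concern.** With P defined as failure, a superior device has P_T below P_C. The rejection rule asks for P_T above P_C. Because Ha is two-sided, the rejection sentence is the only place where either document ties the primary claim to a direction, and that direction is harm.

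The rule decides whether a pivotal trial meant to support a premarket approval application has met its primary objective. Read literally, a result that goes as planned fails the pre-specified criterion, and a significantly worse result passes it. If the wording is first noticed once results are known, turning the inequality round becomes a post-hoc change to the primary decision rule, however obvious the intent. Made beforehand, it is a routine clarification.

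The wording may also carry into the secondary tests. SAP 9.4.5 and 9.4.6 analyse AF freedom in the manner of the primary endpoint, and steps 2 and 4 of the fixed sequence in SAP 9.2 refer back to Section 9.1.

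**Working it through.** **Inputs.** From Protocol 9.2 and SAP 4: success 65% (treatment) and 40% (control), two-sided alpha 0.05, power 80%, allocation 2:1, drop-out 10%, N = 102:51 = 153. In terms of P as defined, the design has P_T = 1 − 0.65 = 0.35 and P_C = 1 − 0.40 = 0.60.

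**Step 1: reproduce the planned sample size.** Pooled-variance formula for two proportions, no continuity correction, control size n and treatment size 2n:

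n = [z(0.975)·√(1.5·p̄(1−p̄)) + z(0.80)·√(0.40·0.60 + 0.65·0.35/2)]² / 0.25², with p̄ = (0.40 + 2·0.65)/3 = 0.5667

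= [1.960·0.6069 + 0.8416·0.5948]² / 0.0625 = 45.7, rounded up to 46.

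This gives 46 control and 92 treatment subjects, 138 evaluable. Then 138/0.9 = 153.3, in line with the stated 153. The design was therefore powered for P_T below P_C.

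**Step 2: compare the rule with the definition.**

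| Element | What it implies |
|---|---|
| P = percentage failing | lower is better |
| Objective: superior on success | P_T < P_C |
| Design: 65% vs 40% success | P_T = 35%, P_C = 60%, so P_T < P_C |
| Rejection rule | estimated P_T > P_C |

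The last row contradicts the other three.

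**Step 3: size.** Failure counts are taken as independent binomials. Every possible 2×2 table is enumerated and those with uncorrected chi-square p < 0.05 are split by the sign of estimated P_T − P_C.

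| N (T:C) | True failure T vs C | Written rule (P_T > P_C) | Corrected rule (P_T < P_C) |
|---|---|---|---|
| 92:46 | 35% vs 60% (design) | 8.9 × 10⁻⁷ | 80.2% |
| 92:46 | 60% vs 35% (device worse) | 79.4% | 7.5 × 10⁻⁷ |
| 102:51 | 35% vs 60% (design) | 4.4 × 10⁻⁷ | 84.0% |
| 102:51 | 60% vs 35% (device worse) | 83.2% | 3.5 × 10⁻⁷ |
| 102:51 | 60% vs 60% (no difference) | 2.6% | 2.5% |

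Only the corrected rule recovers the planned 80% power.

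**Step 4: worked example at 102:51.** Using χ² = N(ad − bc)² / (product of the four margins):

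- Failures 36/102 (35.3%) vs 31/51 (60.8%): 153·(36·20 − 66·31)² / (102·51·67·86) = 8.98, p = 0.003. The result clearly favours the device, yet the written rule is **not** met.
- Failures 61/102 (59.8%) vs 18/51 (35.3%): 153·(61·33 − 41·18)² / (102·51·79·74) = 8.18, p = 0.004. The result clearly favours control, yet the written rule **is** met.

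**The case against.** The strongest reply is that nobody could be misled. The objective and the sample size make the intended direction plain, and the rejection sentence itself rejects only in favour of a two-sided Ha. The word superiority comes from the opening sentence of the section, so calling a worse device superior requires joining two sentences. The later p ≤ 0.05 sentence would let a favourable difference be called significant, with its direction visible in the success percentages by arm.

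Much of this stands. It is a drafting error, not a flaw in design, and the section contradicts itself more than it rules out a favourable conclusion. But the p ≤ 0.05 sentence never says when superiority is attained. That leaves the reversed condition as the only criterion with a direction, in a section whose stated purpose is to determine superiority.

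A second objection is that 92:46 is not the planned denominator, because the ITT analysis in SAP 9.1 keeps subjects with missing outcomes and, under SAP 7.2, counts them as failures. That is fair. With no missing data, 102:51 applies and the corrected rule has 84.0%. If 10% of each arm were missing and counted as failures (an assumption), failure becomes 0.10 + 0.90·0.35 = 41.5% and 0.10 + 0.90·0.60 = 64%, and the corrected rule has about 74%. The written rule is then met with probability of about 1.6 × 10⁻⁶. The denominator moves the power figure but not the finding.

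A third objection is that the mismatch between < and ≤ has no effect. This is correct: no possible table at 102:51 or 92:46 gives an uncorrected chi-square p-value of exactly 0.05. The mismatch is editorial.

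**Conclusion.** The concern holds. In both documents the rejection rule is reversed relative to the documents' own definition of P, and SAP 13 does not correct it. Applied literally at the design effect, the rule is met less than once in a million trials, against 80.2% (92:46) or 84.0% (102:51) for the corrected rule. With the effect mirrored, so that the device is worse, the written rule is met in 79.4% or 83.2% of trials. These figures assume independent binomial outcomes, the planned rates and the uncorrected chi-square test. The contradiction itself depends on none of these assumptions.

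The intended direction is not in doubt, and sample size, alpha and data collection are unaffected. It is still a must-fix item, because it is the pre-specified criterion for the primary claim and a trial that succeeds as planned would not satisfy it as written.

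**What to change.** In SAP 9.1 and Protocol 9.4, state that H0 is rejected and superiority concluded if p < 0.05 and the estimated P_T is less than P_C. Alternatively, redefine P, P_T and P_C as success rates throughout both sections and keep the present inequality. Do one or the other, not both.

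As tidying, use p < 0.05 in both sentences of SAP 9.1 and make the closing sentence refer to the directional rule. Confirm that the corrected direction applies to the AF-freedom tests in SAP 9.4.5 and 9.4.6 and to steps 2 and 4 of SAP 9.2.

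The cost is about one sentence in each document. The change should be made and dated before the sponsor is unblinded.

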9.2 Multiplicity Adjustment

The fixed-sequence procedure[1,2] will be used to evaluate the following secondary endpoints. Each of these tests will be tested at the same significance level ($\alpha=0.05$) in this predetermined order. Each endpoint is only tested if the prior endpoint is successful ($p \leq 0.05$). This procedure does not inflate the Type I error rate since the sequence is prospectively specified and no further testing is performed once an endpoint in the sequence fails to show significance ($p > 0.05$)[2]. All tests will be performed on the ITT population. If sufficient data have not been collected during this study to permit the evaluation of a given endpoint, that endpoint should be skipped and the subsequent endpoint evaluated:

- 1) Achievement of $\geq 90\%$ reduction in baseline AF burden at 12 months post-procedure, where subjects with new or increased dosage of Class I/III AADs during the efficacy evaluation period are categorized as not achieving $\geq 90\%$ reduction, using the Fisher's Exact test as described in Section 9.4.1.

- 2) AF freedom during efficacy evaluation period, using the chi-square or Fisher's Exact test as described in Sections 9.4.5 and 9.1, where subjects with new or increased dosage of Class I/III AADs during the efficacy evaluation period are categorized as not achieving AF freedom.
- 3) Achievement of $\geq 90\%$ reduction in baseline AF burden at 12 months post-procedure, regardless of Class I/III AAD usage, using the Fisher's Exact test as described in Section 9.4.1.
- 4) AF freedom during efficacy evaluation period, using the chi-square or Fisher's Exact test as described in Sections 9.4.5 and 9.1, regardless of Class I/III AAD usage.
- 5) Change in AFSS composite score at 12 months post-procedure, using an ANCOVA model as described in Section 9.4.3.
- 6) Change in SF-36 physical health composite score at 12 months post-procedure, using an ANCOVA model as described in Section 9.4.2.
- 7) Change in SF-36 mental health composite score at 12 months post-procedure, using an ANCOVA model as described in Section 9.4.2.
- 8) Change in distance walked during six-minute walk test at 12 months post-procedure, using an ANCOVA model as described in Section 9.4.4.
- 9) Change in left ventricular ejection fraction (LVEF) at 6 months post-procedure, as described in Section 9.5.2.
- 10) Atrial remodeling assessed by a decrease in left atrial size at 6 months post-procedure, as described in Section 9.5.3.
- 11) Freedom from AF/AFL/AT requiring intervention (emergency visits, cardioversion, urgent care visit, re-ablation, etc.), data permitting.
- 12) Achievement of $\geq 75\%$ reduction in baseline AF burden at 12 months post-procedure, where subjects with new or increased dosage of Class I/III AADs during the efficacy evaluation period are categorized as not achieving $\geq 75\%$ reduction, using the Fisher's Exact test as described in Section 9.4.1.
- 13) Achievement of no more than 12% AF burden at 12 months post-procedure, where subjects with new or increased dosage of Class I/III AADs during the efficacy evaluation period are categorized as not achieving $\leq 12\%$ AF burden, using the Fisher's Exact test as described in Section 9.4.1.
- 14) Freedom from stroke-relevant AF/ AFL/AT-duration (cutoff of 1 hour), data permitting.
- 15) Regression of AF: conversion of persistent to paroxysmal AF, data permitting.
- 16) Prevention in AF progression: time to first episode of persistent AF, data permitting.

Multiplicity tests #1-16 are based on the 12 month data analyses, and will be performed at that time. The following multiplicity tests are based on data collected at the 18 month visit. Therefore, they will be performed after data collection and cleaning is completed for the 18 month visit. As described above, these endpoints will only be evaluated using the fixed-sequence procedure if all of the prior endpoints are significant.

- 17) Success or failure to achieve a 90% reduction from baseline AF burden with and without Class I/III AADs at 18 months post-procedure, where subjects with new or increased dosage of Class I/III AADs during the efficacy evaluation period are categorized as not achieving $\geq 90\%$ reduction, as described in Section 9.5.1.
- 18) Change in number of hospitalizations for the 12 months post-procedure period (6 months to 18 months post- procedure) compared to the number of hospitalizations in the 12 months prior to the procedure, as described in Section 9.5.4, date permitting.
- 19) Change in rhythm disturbance treatments (e.g. electrical or pharmacological cardioversion, AAD therapy, supraventricular ablative therapy) 12 months post-procedure period (6 to 18 months post-procedure) compared to 12 months prior to the procedure, as described in Section 9.5.5, data permitting.

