9.5.8 Freedom from AF/AFL/AT Requiring Intervention

Freedom from AF/AFL/AT requiring intervention (emergency visits, cardioversion, urgent care visit, re-ablation, etc.) will be analyzed as described for the primary efficacy analysis, data permitting. Further details of the analysis will be finalized pending availability and usability of appropriate data.

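### SAP 9.2 puts no primary gate in front of the secondary sequence, so error is held at 0.05 within the chain but not across the primary and secondary endpoints together

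*SAP*

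**What the plan says.** SAP 9.1 tests the primary endpoint with a "chi-square test using a two-sided alpha of 0.05 to determine if superiority of the treatment arm is attained".

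SAP 9.2 then sets out a 19-step fixed sequence, which "will be used to evaluate the following secondary endpoints". On the level it says "Each of these tests will be tested at the same significance level", namely 0.05. Step 1 is achievement of at least a 90% "reduction in baseline AF burden at 12 months post-procedure, where subjects with new or increased dosage of Class I/III AADs" count as failures; it is tested with Fisher's exact test. The passing rule is "Each endpoint is only tested if the prior endpoint is successful", with success defined as p no greater than 0.05. SAP 6.5 makes tests two-sided unless otherwise noted. The justification given is "This procedure does not inflate the Type I error rate since the sequence is prospectively specified" and testing stops at the first non-significant step.

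If too little data were collected to evaluate an endpoint, "that endpoint should be skipped and the subsequent endpoint evaluated". Tests 11, 14, 15, 16, 18 and 19 are each marked as conditional on the data allowing them (test 18 with a misprint). For tests 11 and 14–16, SAP 9.5.8 to 9.5.11 each add: "Further details of the analysis will be finalized pending availability and usability of appropriate data". Tests 17–19 are to be run only if every earlier endpoint is significant.

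SAP 6.4 on multiplicity only points to 9.2. Protocol 9.5 adds no gate.

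**The concern.** The primary does not appear in the sequence, and step 1 has nothing before it. Someone following the text would test step 1 at full alpha after a failed primary and could present a significant result as a confirmatory finding. The protocol's Study Purpose section says the data are expected to support a premarket approval application, so it matters which claims are formally protected.

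Two further features of 9.2 deserve attention. Success is defined by a two-sided p-value without a direction, so a step that significantly favours catheter ablation counts as passed. And the error-control argument rests on the sequence being specified in advance, although some of its later steps are not fully specified.

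**Working it through.** **Inputs.** From the SAP: primary at two-sided 0.05 (9.1); each chain step at 0.05 (9.2); 19 steps; 102:51 subjects (section 4). Assumed: the correlation between the primary and step 1 statistics, and the common success rates used for Fisher's test. The documents give neither.

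**The plan's own figures.** In a fixed order, any false rejection requires rejecting the first true null in the list, which is tested once at 0.05. The chain's error is therefore at most 0.05. Simulating all 19 steps under the null gave 0.049 to 0.051. The statement in 9.2 is correct for the secondary family. The sample size also reproduces: 40% vs 65%, two-sided 0.05, 80% power and 2:1 allocation give 46 + 92 = 138, and 138/0.9 = 153.3 against the stated 153.

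**Primary plus ungated chain, both nulls true.**
- Independent: 1 − 0.95² = 0.0975.
- Correlated: 1 − P(|Z₁| < 1.96 and |Z₂| < 1.96), bivariate normal.

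| Assumed correlation | Chance of any false rejection |
|---|---|
| 0 | 0.0975 |
| 0.5 | 0.091 |
| 0.7 | 0.083 |
| 0.8 | 0.078 |
| 0.9 | 0.070 |
| 0.99 | 0.057 |

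- Favourable false claims only, independent: 1 − 0.975² = 0.049, against 0.025 for a single test.
- With a gate on the primary: 0.050 at every correlation (simulated).

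**Fisher's test at step 1.** Enumerating its true size at 102:51, for common success rates of 40% to 80%, gives 0.038 to 0.040. Combined with the exact size of the chi-square test and assuming independence, the total is 0.084 to 0.089. At 92:46 it is 0.086 to 0.092.

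**Direction.** Suppose step 1 is truly worse on EPi-Sense-AF, with an assumed mean z of −4. It passes about 98% of the time. False rejections among steps 2 to 19 then total 0.049 and false favourable claims 0.025 (steps independent). The wrong-way pass does not push error above 0.05. Referring to 9.1, as steps 2 and 4 do, does not supply a direction: its clause requires the treatment arm's estimated P to exceed the control arm's, and P is defined there as a failure rate, so as printed it favours control.

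**Skips.** Skips decided without sight of outcomes leave the chain at 0.05 (simulated 0.050 with 30% of steps dropped at random). If skips followed results, the worst case with independent true nulls, all other earlier steps having passed, would be:
- test 11, then 12: 1 − 0.95² = 0.0975;
- tests 14–16, then 17: 1 − 0.95⁴ = 0.185;
- the six conditional tests: 1 − 0.95⁶ = 0.265.

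**The case against.** The strongest reply is that a primary gate is understood. It may be intended, but 9.2 spells out the gate for each later step, and again for tests 17–19, and says nothing for step 1. An understood gate should be written.

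A reader might infer that the no-inflation sentence is simply false. The text does not support that: the sentence describes the procedure as applied to the secondary endpoints, and for them it is true. It is silent on the primary.

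A reader might also infer that the p-only rule and the skips inflate error, or that skips are at the sponsor's discretion. Neither follows. The p-only rule leaves two-sided error at or below 0.05, and a result favouring control could not support a benefit claim on that endpoint, since SAP 2.1.3 frames the secondary objectives as demonstrating efficacy of EPi-Sense-AF. The skip rule does state a criterion, and it concerns data collection rather than results. What it lacks is a threshold, a decision-maker and a deadline.

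Nor are tests 11 and 14–16 undefined. Tests 11 and 14 follow the primary analysis, 14 has a one-hour cutoff, and 15 and 16 have a named population. All four sit behind ten earlier steps and cannot affect tests 1–10.

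Finally, 9.75% is a ceiling. Both endpoints fail a subject for new or increased Class I/III drugs, and the 12-month Holter feeds both, so positive correlation is likely. This stands, and it reduces the size of the problem without removing it.

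**Conclusion.** The concern holds in a limited form. As written, the primary and step 1 are each tested at two-sided 0.05 with no link between them, so error is controlled within the secondary chain but not across primary plus secondaries. The upper limit is 9.75% under independence, about 9.1% at correlation 0.5 and 7.0% at 0.9, and somewhat less given the conservatism of Fisher's test (8.4% to 8.9% under independence at 102:51). These figures take both nulls as true. The primary test itself is unaffected.

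The missing direction is a defect in what a passed step means, not a source of two-sided error. The open skip criterion and unfinished analyses weaken the claim of prospective specification. They would raise error only if skips or definitions were chosen with knowledge of results. The documents do not suggest that this is intended, but they do not exclude it: the trial is open-label, SAP 11 allows ad hoc analyses, and the skip decision has no pre-lock deadline of the kind that SAP 7.4.3 and 7.4.6 set for drug and ablation classification.

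**What to change.** In SAP 9.2:

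1. State that step 1 is tested only if the primary is significant in favour of EPi-Sense-AF. Write the direction out here rather than by reference to 9.1, and correct the direction clause in 9.1.
2. Define success at each step as p no greater than 0.05 with the estimate favouring EPi-Sense-AF.
3. Fix the evaluable endpoints, their definitions and any skips for tests 11, 14–16, 18 and 19 before database lock and unblinding of the sponsor, with a stated sufficiency rule, or move these tests out of the sequence. Because the skip rule covers all 19 tests, the sufficiency rule should too.
4. Say how a skipped step counts towards the requirement that every earlier endpoint be significant before tests 17–19.

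Cost: formal secondary claims are lost if the primary fails. Items 1, 2 and 4 take a few sentences. If tests 11 and 14–16 stay in the sequence, SAP 9.5.8 to 9.5.11 must be completed as well. The sample size stays at 153.
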